4.3.1.2 Unsolicited Non-serious Adverse Events (AEs)

4.3.1.2.1 Presence

An observation will be considered an event if it has at least a verbatim term and is not a Grade 0 intensity event. Grade 0 events should be included in the listing “Unsolicited non-serious adverse events not included in the safety analysis.”

4.3.1.2.2 Intensity

Intensity for unsolicited non-serious AEs will be derived according to the following classification: None, Grade 1, Grade 2, Grade 3, or Missing.

If the unsolicited non-serious AE is measurable and its preferred term (PT) is part of the list of solicited reactions, then the measurement is derived based upon and following the same rule as the intensity scales defined in the protocol for that measurable injection site or systemic reaction. Note that the intensity could be considered “None” (not a reaction) in the analysis despite being

considered a reaction by the investigator (e.g., swelling measurement > 0 mm but < 25 mm in adults).

Intensity for the other unsolicited non-serious AEs will correspond to the value reported in the eCRF.

The maximum intensity corresponds to the highest intensity for a unique term.

4.3.1.2.3 Last Vaccination

Last vaccination before an unsolicited non-serious AE is derived from the visit numbers provided in the clinical data base and is calculated as follows:

- If an unsolicited non-serious AE has a non-missing visit number, the visit number should be used to determine the last vaccination before the unsolicited non-serious AE
- If the visit number is missing, then the start date should be used to determine the last vaccination before the unsolicited non-serious AE.

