- 10) Remind the subject to notify the site in case of an SAE or pregnancy (for woman of childbearing potential).
- 11) Complete the relevant source document information and CRF pages for this visit.

V06 (14 [± 3] days after VAC5): Collection of Safety Information and Blood Sample

- 1) Review the DC3 with the subject, including any adverse events, medications, or therapy that occurred since vaccination by Investigator or delegate. The subject will continue using the DC1 to collect safety information until the next visit.
- 2) Conduct a physical examination.

- 3) Obtain the fourth 5mL blood sample (see [Section 7.1](#) for detailed instructions regarding the handling of blood samples).
- 4) Remind the subject to notify the site in case of an SAE or pregnancy (for woman of childbearing potential).
- 5) Complete the relevant source document information and CRF pages for this visit.

V07 (28 [± 3] days after VAC5): Collection of Safety Information

- 1) Review and collect the DC3 with the subject, including any adverse events, medications, or therapy that occurred since vaccination by Investigator or delegate.
- 2) Conduct a physical examination.
- 3) Give the subject with the memory aid (MA) to record any SAEs or AESIs that may occur during the 6-month safety follow-up.
- 4) Remind the subject to notify the site in case of an SAE or pregnancy (for woman of childbearing potential).
- 5) Complete the relevant source document information and CRF pages for this visit.

V08 (6 months [± 14] days] after VAC5): Collection of Safety Information and Blood Sample

- 1) Review MA by Investigator or delegate.
- 2) Obtain the fifth 5 mL blood sample (see [Section 7.1](#) for detailed instructions regarding the handling of blood samples).
- 3) Complete the relevant source document information, complete the termination record of the CRF, and enter the subject's termination information in the IVRS / IWRS.

SAEs and AEs That Are Related to Vaccination or That Led to Discontinuation:

At any time during the study, a subject who experiences an SAE or an AE must be followed if *either* of the following is true:

- The SAE or AE is considered by the Investigator to be related to vaccination, and is not resolved by the end of the subject's participation in the trial
- The subject has been discontinued from the trial because of the SAE or AE

Any such subject must be followed until the condition resolves, becomes stable, or becomes chronic.

Pregnancy cases*

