4.3.1.2.4 Time of onset

Time of onset is derived from the start date of the unsolicited non-serious AE provided in the clinical database and the date of last vaccination:

- start date of the unsolicited non-serious AE – date of previous vaccination

The time of onset should be considered as missing only if one or both of the dates are missing or partially missing.

An AE with missing time of onset will be considered to have occurred just after the vaccination indicated by the visit number, so will be included in these tables. Note: Unsolicited non-serious AE that occurred before vaccination (negative time of onset) will not be included in analysis, but will be listed separately.

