|-----------------|--|----------------|
| Post-dose 3,4,5 | | D0-D3 D4-D7 |
|-----------------|--|----------------|

- Range of number of days of occurrence categories are in Table 5.3

Table 5.3: Range of Number of Days of Occurrence Categories for Solicited Reactions during the solicited period

| | Injection Site Reactions | Systemic Reactions |
|------------------|------------------------------------|--------------------------|
| Post-dose 1 | 1 - 3 days 4 - 7 days 8 days | 1 - 3 days 4 days |
| Post-dose 2 | | 1 - 3 days 4 - 5 days |
| Post-dose 3, 4,5 | | 1 - 3 days 4 - 7 days |

Solicited reaction after any injection

“After any injection” means after the five scheduled vaccine injections, and at least after the first vaccine injection (D0).

The solicited reaction will be presented after any injections according to:

- Overall occurrence over the D0-D7 period for injection site reactions or between vaccinations for systemic reactions (up to D7 for the last 2 vaccinations)
- Time of onset period
- Intensity grade: the maximum intensity grade will be computed during the solicited period for all solicited reactions and overall for on-going solicited reactions.

30-minutes Post-Vaccination Observation Period

Unsolicited systemic AEs occurring within 30 minutes after each vaccination will be presented in summary safety tables, analyzed according to their nature (SOC and PT of the MedDRA classification) and will be listed.

Unsolicited Adverse Events

The unsolicited non-serious AEs will be analyzed

- “Between the first and the second vaccine injection”, which corresponds to AEs reported at V02 and occurring after the first vaccine injection †

† For subjects interrupting their vaccination schedule after the first injection, unsolicited AEs until 28 days after the first injection are collected at visit V02

- “Between the second and the third vaccine injection”, which corresponds to AEs reported at V03 and occurring after the second vaccine injection [†]
- “Between the third and the fourth vaccine injection”, which corresponds to AEs reported at V04 and occurring after the third vaccine injection [§]
- “Between the fourth and the fifth vaccine injection”, which corresponds to AEs reported at V05 and occurring after the fourth vaccine injection ^{**}
- “Within 28 days after the fifth vaccine injection”, which corresponds to AEs reported at V07 and occurring after the fifth vaccine injection

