- “Within 28 days after any vaccine injection”, which corresponds to AEs belonging to any of the five above categories

An AE reported with an onset > 28+3 days after an injection will not be included in the analysis, but will be listed separately. The unsolicited AEs will be summarized in the safety overview and analyzed according to their nature (SOC and PT of the MedDRA classification), causality (relationship to the vaccine injection as assessed by the investigator), time of onset, duration and maximum intensity.

The occurrence of any unsolicited non-serious AE will be presented after any and each injection according to:

- *Maximum intensity:*

- Missing
- Grade 1
- Grade 2
- Grade 3

- *Time of onset categories*

- Missing
- D0-D3
- D4-D7
- D8-D14
- >=D15

[†] For subjects interrupting their vaccination schedule after the second injection, unsolicited AEs until 28 days after the second injection are collected at visit V03

[§] For subjects interrupting their vaccination schedule after the third injection, unsolicited AEs until 28 days after the first injection are collected at visit V04

^{**} For subjects interrupting their vaccination schedule after the fourth injection, unsolicited AEs until 28 days after the second injection are collected at visit V05

- *Maximum duration:*

- Missing
- 1 - 3 days
- 4 - 7 days
- 8 - 14 days
- 15 days or more

SAEs and AESIs

The SAEs and AESIs occurred during the study will be analyzed on the following periods:

1. vaccination period: after any vaccination period (D00-D56[+3D])
2. during the six-month safety follow-up period (all SAEs and AESIs from D56[+3D])

SAEs will be analyzed according to their causality (relationship to vaccine injection as assessed by the investigator), seriousness, outcome and nature (SOC and PT of the MedDRA classification).

AESIs will be summarized and analyzed according to their nature (SOC and PT of the MedDRA classification) and causality.

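### Assigning unsolicited non-serious AEs to a dose by visit number, ahead of a known start date, can drop late-labelled events from the per-dose and any-dose tables; the interval wording is also inconsistent for V06 and immediate events

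*SAP*

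**What the plan says.** SAP 4.3.1.2.3 fixes the order of evidence for the vaccination preceding an unsolicited non-serious AE. First, "If an unsolicited non-serious AE has a non-missing visit number, the visit number should be used to determine the last vaccination before" the event. Only then: "If the visit number is missing, then the start date should be used to determine the last vaccination". The term visit number is not defined.

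SAP 4.3.1.2.4 takes time of onset as start date minus the date of that vaccination, and adds: "Unsolicited non-serious AE that occurred before vaccination (negative time of onset) will not be included in analysis, but will be listed separately". An event whose onset is missing is kept, under the vaccination that its visit number indicates.

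SAP 5.1.2.2.1 sets five intervals, each with two conditions: a named visit and onset after the matching dose. The first is the interval "which corresponds to AEs reported at V02 and occurring after the first vaccine injection"; the second, "which corresponds to AEs reported at V03 and occurring after the second vaccine injection". The third and fourth follow the pattern with V04 and V05. The fifth is the interval "which corresponds to AEs reported at V07 and occurring after the fifth vaccine injection". The any-dose category is the one "which corresponds to AEs belonging to any of the five above categories".

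The same section uses all subjects vaccinated at the dose (or at least once) as the denominator for unsolicited events, and gives avoidance of under-estimated incidence as its reason for how denominators are chosen. SAP 4.3.1 sets a general window of 28 + 3 days after vaccination, with no visit condition. At V06, Protocol 5.1.4 tells sites: "Review the DC3 with the subject, including any adverse events, medications, or therapy that occurred since vaccination", and to complete the CRF pages for that visit.

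**The concern.** Protocol 9.2.2 defines the unsolicited systemic AE endpoint by time relative to injections, not by when the site records the event. The SAP lets a recording label decide the dose even when a complete start date is available, then tests the start date against the dose so chosen. If label and date disagree, the event is removed, not reassigned.

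Late labelling is plausible early on. The first three injections fall on D0, D3 and D7, and one diary card (DC1) covers all of them and is collected only at V04. The safety profile is one of the inputs to choosing the VRVg-2 dosage (Protocol 1.4 and section 12), and the planned output is descriptive rates by dose. A rule that removes dated post-vaccination events acts directly on those rates.

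**Working it through.** **Inputs.** Nominal injection days are 0, 3, 7, 14 and 28 (Protocol Table 5.3). The SAP gives no explicit map from visit number to last vaccination. The one used here is inferred from the pairing in 5.1.2.2.1: V02 to VAC1, V03 to VAC2, V04 to VAC3, V05 to VAC4, V07 to VAC5. V06 also maps to VAC5, because no injection follows it.

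**Formula (SAP 4.3.1.2.4).** Onset = start day − day of the last vaccination. A negative value means listed only.

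**Worked case.** An AE starts on D2 and is labelled V03. By visit number the last vaccination is VAC2 on D3, so onset = 2 − 3 = −1 and the event is excluded. It fails interval 1 (not reported at V02) and interval 2 (not after VAC2), so it is also outside their union. By start date the last vaccination is VAC1 on D0, so onset = 2 − 0 = 2 and the event belongs to interval 1.

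**Other cases.**

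| Start day | True dose | Label | Onset by visit number | Interval met in 5.1.2.2.1 |
|---|---|---|---|---|
| D1 | 1 | V02 | 1 − 0 = 1 | first |
| D1 | 1 | V03 | 1 − 3 = −2 | none |
| D5 | 2 | V04 | 5 − 7 = −2 | none |
| D10 | 3 | V05 | 10 − 14 = −4 | none |
| D20 | 4 | V06 | 20 − 28 = −8 | none |
| D35 | 5 | V06 | 35 − 28 = +7 | none |
| D35 | 5 | V07 | 35 − 28 = +7 | fifth |

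After doses 1 to 4, every late-labelled dated event checked fails both rules. The D35 event labelled V06 is different. Under 4.3.1.2.3 and 4.3.1.2.4 it is a dose 5 event with positive onset, inside the 28 + 3 day window; only the fifth interval's wording leaves it out. The SAP's rules disagree with each other there.

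**Immediate events.** VAC2 is given at V02. An AE within 30 minutes of it, recorded at V02, starts after the first injection and is reported at V02. It therefore literally meets interval 1, although it followed dose 2. The same holds for doses given at V03 to V05.

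**Missing dates.** Give the D2 event labelled V03 no start date. Onset is then missing, and SAP 4.3.1.2.4 keeps it, under dose 2. SAP 5.3.2.5 goes further and treats onset as missing when only the stop date is absent, which conflicts with 4.3.1.2.4. On that rule, an event with a start date but no stop date is kept and a fully dated one is dropped.

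**Effect on a rate.** The plan's only related figures are the exact 95% CIs for AE rates with 80 subjects (Protocol Table 12.2, SAP Table 5.5). All five rows reproduce with Clopper-Pearson limits. With the denominator fixed, and assuming the lost event was the subject's only one in that category:

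- 8/80 = 10.0% (4.4; 18.8). One subject lost: 7/80 = 8.75% (3.6; 17.2).
- 16/80 = 20.0% (11.9; 30.4). Two subjects lost: 14/80 = 17.5% (9.9; 27.6).
- In a group of 40, 4/40 = 10.0% (2.8; 23.7). One subject lost: 3/40 = 7.5% (1.6; 20.4).

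The numbers lost are illustrative; the documents supply none.

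**The case against.** The strongest reply is that visit number may not mean the visit at which the site heard of the event. Footnotes in SAP 5.1.2.2.1 say that, for a subject who stops after the first injection, events up to 28 days later are collected at V02, although V02 is D3. That reads like a nominal label tied to a dose. If so, a D2 event discovered at V03 would be entered under V02, get onset +2 and be counted, and most of the loss would not arise. This stands as a real ambiguity. It does not remove the point: the interval definitions speak of the visit where events are reported, and two programmers could produce different tables from the same text.

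Second, safeguards exist. The diary is reviewed first at V02 to V05, before the next injection (Protocol 5.1.4); consistency checks with queries follow (Protocol 11.2); and a blind review precedes database lock (Protocol 11.3, SAP 5.6). These could catch a mismatch between label and date, but neither document says that such a mismatch is queried or how it is resolved.

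Third, putting the visit first has a use. Protocol 9.2.3.3 lists start and stop dates for these events but no clock time, so on an injection day the date alone cannot tell an event before the injection from one after it. This stands, and it shapes the fix.

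Fourth, the same rule applies to every randomized group and safety assessors are blinded, so no bias between groups is shown. That also stands; what is affected is the absolute and per-dose rates.

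A reader might infer that every post-dose-5 event entered at V06 disappears, which with uniform onset over 28 days would be up to 14/28, or half. The documents do not support that. SAP 4.3.1.2.3 sends a V06 event to dose 5, the 28 + 3 day window has no visit condition, and DC3 is checked at V06 but collected at V07, which may be why only V07 is named.

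**Conclusion.** The point holds for unsolicited non-serious AEs with a complete start date, after doses 1 to 4, that carry a later visit label, provided the visit number is the reporting visit. Such events leave the per-dose and any-dose tables and remain only in a listing. A lost event can lower incidence but never raise it, against the SAP's own aim of avoiding under-estimation. The rule also keeps a less complete record and drops a complete one.

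The size is unknown. A reader might assume that some 5 to 10% of early events are reported a visit late and so vanish, but nothing in the documents supports that or any other rate.

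The V06 wording and the immediate-event overlap are internal inconsistencies: the first is not a proven loss, and the second concerns which dose an event is counted under.

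Nor is it true that all late-reported events are lost. Those without a usable start date are kept, though under the later dose. Solicited reactions use daily records. SAEs are summarised by period (SAP 5.1.2.2.1), and AESIs, which Protocol 9.2.3.5 has reported as SAEs, likewise. SAP 4.3.1.3.1 does apply the same last-vaccination method to SAEs, so an SAE's dose attribution could be affected even though its period count is not.

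**What to change.** - In SAP 4.3.1.2.3, when the start date is complete and is not an injection day, take the last vaccination as the latest injection before that date.
- When the start date is an injection day, use the immediate flag and the visit label to decide whether the event came before or after the injection.
- Use the visit number alone only when the start date is missing or partial.
- Define visit number: reporting visit, or nominal label tied to a dose.
- Define the five intervals in 5.1.2.2.1 by onset relative to injections. At the least, name V06 together with V07 in the fifth.
- Limit the negative-onset exclusion in 4.3.1.2.4 to events starting before VAC1.
- Align 5.3.2.5 with 4.3.1.2.4 on whether a missing stop date makes onset missing.

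The cost is SAP wording and somewhat more derivation logic, using fields already collected. Some ambiguity stays for events on an injection day that are not flagged as immediate, because no clock time is listed for them.

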4.3.1.2.4 Time of onset

Time of onset is derived from the start date of the unsolicited non-serious AE provided in the clinical database and the date of last vaccination:

- start date of the unsolicited non-serious AE – date of previous vaccination

The time of onset should be considered as missing only if one or both of the dates are missing or partially missing.

An AE with missing time of onset will be considered to have occurred just after the vaccination indicated by the visit number, so will be included in these tables. Note: Unsolicited non-serious AE that occurred before vaccination (negative time of onset) will not be included in analysis, but will be listed separately.

4.3.1.2.5 Duration

Duration is derived from the start and stop dates of the unsolicited non-serious AE provided in the clinical database:

- stop date of unsolicited non-serious AE - start date of unsolicited non-serious AE + 1.

The duration should be considered as missing only if one or both of the start and stop dates of the unsolicited non-serious AE is missing or partially missing.

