Subjects are to measure body temperature once per day, preferably always at the same time. The optimal time for measurement is the evening, when body temperature is the highest. Temperature is also to be measured at the time of any apparent fever. The observed daily temperature and the route of measurement are to be recorded in the DC/MA, and the highest temperature will be recorded by the site in the CRF. The preferred route for this trial is oral. Pre-vaccination temperature is also systematically collected on the source document. Tympanic thermometers must not be used.

9.2.3.3 Unsolicited Non-serious Adverse Events From Day 0 to Day 28 After Each Vaccination

In addition to recording solicited reactions, subjects will be instructed to record any other medical events that may occur between each vaccination and during the 28-day period after the last vaccination. Space will be provided in the diary card for this purpose.

For each unsolicited non-serious AE, the following information is to be recorded:

- Start and stop dates^a
- Intensity of the event:
 - For measurable unsolicited non-serious AEs that are part of the list of solicited reactions, the size of the AE as well as the temperature for fever will be collected and analyzed based on the corresponding scale used for solicited reactions (see [Table 9.1](#) and [Table 9.2](#))
 - Other unsolicited non-serious AEs will be classified according to the following intensity scale:
 - Grade 1: No interference with activity
 - Grade 2: Some interference with activity
 - Grade 3: Significant; prevents daily activity
- Action taken for each AE, if any (e.g., medication)

The action taken by the subject to treat any **unsolicited AEs** will be classified in the CRF using the following scale:

0: None

1: Medication (self-medication with an existing prescription or over-the-counter medication)

2: Health care provider contact (no new medication prescribed)

^a The stop date of all related AEs will be actively solicited. For other events, the investigator will provide the stop date when it becomes available. AEs for which no stop date was obtained during the course of the trial will be considered as ongoing at the end of the trial.

3: Health care provider contact and prescription of a new medication (health care provider instructed subject to take a new medication, either an over-the-counter medication or one requiring a written prescription)

- Whether the AE led to study discontinuation

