4.3.1.1.6 Overall Number of Days of Occurrence

If a reaction is ongoing at the end of the solicited period, then the overall number of days of occurrence is derived from the daily intensities and the stop date of the reaction after the end of the solicited period. The overall number of days of occurrence is:

- (stop date – last vaccination date) + (number of days of occurrence within the solicited period) – length of the solicited period + 1

If the stop date is missing or incomplete (contains missing data [MD]), the overall number of days of occurrence will be considered as “Missing”.

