5.3.2.5 Start Date and Stop Date

Missing or partially missing start dates for unsolicited AEs will remain missing and will not be imputed.

Missing or partially missing stop dates for AEs (solicited reactions and unsolicited AEs) will remain missing and will not be imputed.

If either the start or stop date is missing or partially missing, the time of onset will be considered to be missing. Nevertheless unsolicited AEs with missing time of onset will be included in analyses according to the visit collected.

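### Unsolicited AEs with no stop date are tabulated with missing duration, so unresolved events are pooled with lost dates and the longest-duration row is understated

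*SAP*

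**What the plan says.** SAP 4.3.1.2.5 derives the duration of an unsolicited non-serious AE as "stop date of unsolicited non-serious AE - start date of unsolicited non-serious AE + 1". Its rule for absent dates reads "The duration should be considered as missing only if one or both of the start and stop dates" is absent or partial. SAP 5.3.2.5 repeats the principle: "Missing or partially missing stop dates for AEs (solicited reactions and unsolicited AEs) will remain missing and will not be imputed".

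SAP 5.1.2.2.1 (Unsolicited Adverse Events) presents unsolicited non-serious AEs, after each and any injection, by maximum duration in five rows: missing, 1 to 3 days, 4 to 7 days, 8 to 14 days, and 15 days or more. The denominator is all subjects vaccinated at the dose analysed, or vaccinated at least once for the any-dose analysis.

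Protocol 9.2.3.3, footnote a, treats the same empty field differently. Stop dates of related AEs are actively solicited. For other AEs the investigator supplies the date when it becomes available. It then states that "AEs for which no stop date was obtained during the course of the trial will be considered as ongoing" when the trial closes.

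No SAP text carries this ongoing status into the duration of unsolicited AEs.

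**The concern.** A blank stop date can mean two things: the event had not ended, or it ended and the date was not obtained. In the first case the duration is not unknown. It is at least the time from onset to the last visit at which the event was seen to be unresolved. The SAP discards that lower bound and puts both cases in one row.

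For unresolved events, the outcome itself causes the missingness: failure to resolve empties the field that the duration needs. The row meant to show long-lasting events thus loses events because they were long-lasting, and a reader of the table cannot separate them from poor date recording.

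The per-subject maximum adds a second problem. The SAP does not say what happens when one AE has a known duration and another has none. If missing values are ignored, a subject with a 2-day AE and an unresolved AE is shown under 1 to 3 days.

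Duration is a tabulated safety result here, and the Protocol (Section 12) bases the choice of VRVg-2 dosage on the safety profile as well as on immunogenicity.

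**Working it through.** The plan gives no figure to reproduce. The check sets the rules side by side and applies the SAP's own date formula.

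**Inputs**
- Duration = stop − start + 1; missing if either date is absent or partial (SAP 4.3.1.2.5).
- Stop dates are not imputed (SAP 5.3.2.5).
- Top row of the table: at least 15 days; no row for ongoing (SAP 5.1.2.2.1).
- Injection-site and systemic event assessment runs to V07, nominally D56, which is VAC5 + 28 days ± 3 (Table of Study Procedures in the Protocol; SAP Table 3.2).
- The first analysis uses data up to D56 (Protocol 12; SAP 5.4). Protocol 6.5 calls it the primary analysis and breaks the code for it.

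**Step 1. When is an AE open at V07 known to have lasted 15 days?**
Minimum duration = V07 date − start date + 1. At the nominal visit this is at least 15 when start ≤ 56 + 1 − 15 = D42, that is VAC5 + 14 days. Check: 56 − 42 + 1 = 15. With V07 at VAC5 + 25 or VAC5 + 31, the latest qualifying start is VAC5 + 11 or VAC5 + 17.

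**Step 2. Where does each event go?** (assumed examples, nominal V07)

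| AE | Minimum duration | Row under the SAP | Row it supports |
|---|---|---|---|
| Starts D20, documented unresolved at V07 | 56 − 20 + 1 = 37 days | Missing | 15 days or more |
| Starts D50, documented unresolved at V07 | 56 − 50 + 1 = 7 days | Missing | Ongoing at last assessment |
| Starts D20, partial stop date | Not computed | Missing | Missing |

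All three share one row under the SAP. Only the third has a duration about which nothing is recorded reliably.

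**Step 3. Direction.** The SAP rule never places a shorter AE in the *15 days or more* row. It removes subjects whose only AE of that length was unresolved. A subject who also has a resolved AE of 15 days or more stays in the row. Because the denominator is all vaccinated subjects, the row's percentage is either right or too low.

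**Step 4. Size per subject.** If every planned subject is vaccinated, each subject misplaced changes the row by 1/80 = 1.25 percentage points in a VRVg-2 group and by 1/40 = 2.5 points in the VRVg-1 or Imovax Rabies group. How many subjects this concerns cannot be derived from the documents.

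**The case against.** The case for leaving the SAP alone has substance:

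- No AE leaves the analysis. Each still counts in incidence, intensity and causality, and the *Missing* row is displayed, so a shortfall is visible.
- The trial is descriptive and the rule is the same in all five groups.
- SAEs are also analysed by outcome. Related AEs that persist at the end of the trial are followed to disappearance or stabilisation (Protocol 9.2.3.3).
- The two documents can stand together: the Protocol assigns a status and the SAP declines to assign a length.

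All of this stands, and it limits the point to a small improvement. It does not answer the pooling: the table still cannot show which missing durations belong to events known to be unresolved.

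Four stronger readings are tempting, and the documents do not support them.

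1. *Solicited reactions have the same defect.* SAP 4.3.1.1.6 has a similar clause ("If the stop date is missing or incomplete" and so on). But Table 5.3 counts days only within the solicited period, with 8 days as its top category. SAP 4.3.1.1.7 derives ongoing status without a stop date, and no listed table puts solicited reactions in a 15-day row.
2. *The missing durations are exactly the unresolved AEs.* Partial dates are also set to missing. So is a resolved, unrelated AE whose stop date was never obtained; the Protocol's ongoing label for it is a recording convention.
3. *Every AE without a stop date lasted until M7.* Routine event assessment ends at V07, and the memory aid then collects SAEs and AESIs. Later follow-up is specified for related AEs and for those that led to discontinuation. For an unrelated non-serious AE, V08 need not be a visit at which it was seen unresolved.
4. *The understatement can be given as a percentage.* That needs the share of AEs unresolved and the share lasting 15 days or more. The documents give neither, and the table counts subjects, not AEs.

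**Conclusion.** The point holds for unsolicited AEs only. The SAP sets duration to missing whenever the stop date is absent, although the Protocol classes such AEs as ongoing, and the table has no row that keeps the two apart. The *15 days or more* row is understated whenever a subject's only AE of that length is unresolved. At the first analysis this includes any AE that began by about D42 and was still open at V07. The Protocol's ongoing label strictly applies at the end of the trial, but the empty field has the same effect at that earlier lock.

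The size is unknown. The effect should fall mainly on AEs judged unrelated. The conclusion on direction assumes only that some AEs are documented as unresolved at their last assessment. The misplacement into a shorter row is conditional, because the SAP is silent on how the maximum treats missing values. This is a cheap improvement to a tabulated safety result; nothing in the documents shows that it would alter the choice of dosage.

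**What to change.** Change SAP 4.3.1.2.5, with a matching line in 5.3.2.5 and in the maximum-duration list of 5.1.2.2.1:

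- **Minimum duration.** For an unsolicited AE with a complete start date and no stop date, compute: last visit at which the AE was documented as unresolved − start date + 1. That visit is V07 for most non-serious AEs, and later only where follow-up is recorded.
- **Rows.** Count the AE in *15 days or more* if this minimum is at least 15. Otherwise show it in a new row, *ongoing at last assessment*.
- **Missing.** Keep this row for unknown or partial start dates, partial stop dates, and AEs with no documented status.
- **Per-subject maximum.** State that a subject with an ongoing AE is not placed in a shorter row because missing durations are ignored when the maximum is taken.

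No change is needed to SAP 4.3.1.1.6.

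The cost is a few lines of SAP text, one derivation and one table row. The derivation depends on resolution status being recorded at the visit, which the documents do not confirm; where it is not recorded, the AE stays in *Missing*. The downside is that some AEs whose stop dates were merely not obtained may be shown as ongoing, so a table footnote should say so.
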